## 11. Device accountability

All access to the investigational devices used in the clinical investigation is controlled by storage procedures and device accountability logs as described below. The investigational devices must only be used in this clinical investigation and only per the CIP.

Sponsor keeps a device accountability log that states the physical location of all investigational devices from shipment of investigations devices to the investigational site until return of or disposal.

The PI or an authorised designee keeps records documenting the receipt, use and return and disposal of the investigational devices, which includes:

- Date of receipt.
- Identification of each investigational device (batch no./serial no./unique code).
- The expiry date
- The date(s) of use.
- · Subject identification.

The same accountability procedure will count for the comparator product.

### 12. Statement of compliance

The clinical investigation is conducted in accordance with:

- Ethical principles that have their origin in "The Declaration of Helsinki, 1964, last amended at the 64th WMA General Assembly, Brazil, October 2013".
- MDD 93/42/EEC as amended by Directive 2007/47/EC (commonly known as the Medical Device Directive).
- ISO 14155:2011 "Clinical Investigation of medical devices for human subjects Good clinical practices".
- Executive Order on Medical Devices no. 1263 of 15 December 2008 (Bekendtgørelse om medicinsk udstyr nr. 1263 af 15. december 2008)

## 12.1. Ethics committee and regulatory authorities

The CIP and/or other relevant documents are submitted to the appropriate EC and the Danish Medicine Agency. This clinical investigation will not begin until the required approval from this ethics committee and regulatory authority has been obtained. Any amendment to the protocol will be submitted to the same ethics committee and regulatory authority.

### 12.2. Data protection

[figure not shown]
This clinical investigation does not require approval by the Data Protection Agency. Per the Order 410 of 09/05/2012, Exemption from submission to the Data Protection Agency, handling of sensitive personal data in health science research projects is exempted from the requirement for notification and permission from the Data Protection Agency if the project is covered by the Act on Scientific Ethics of Health Science Research Projects and is authorised by a Scientific Committee.

Coloplast A/S is committed to and follows the Data Protection Act. All information collected during this investigation is kept strictly confidential. Subjects are identified by an investigation number and the investigation monitor has limited access to subjects' documentation for source data verification. Any information which could identify a subject remains with the investigator where it is archived with investigation documents. Subjects remain anonymous for data analysis.

Should the investigation require future review, relevant regulatory authorities and ethics committees will be allowed access to all relevant information for audit and inspection purposes.

### 12.3. Indemnity

All subjects are fully covered by Coloplast A/S insurance throughout the investigation:

#### 12.4. Financial conditions

Coloplast A/S will compensate investigator and study nurses for their time and resources spent on the investigation (including overhead for the hospital and administrative costs) as specified in a sponsor investigator contract.

Investigator has no apparent conflict of interest.

This is to compensate for any inconvenience caused during the catheterisations, time used and travel expenses. The remuneration is taxable (B-income)

## 13. Informed consent process

and it is the responsibility of the subject to declare this to Skat.

Written informed consent is obtained from all subjects participating in the investigation after thorough written and verbal information. The informed consent process takes place in a room reserved for ensuring privacy and quiet surroundings at the investigator's department. The subjects will receive both written and verbal information about the possibility of bringing a companion to the visit and to any possible subsequent visits.

The information is given by the investigator or his/her representative in the subjects' native non-technical language. Each subject will be fully informed about the aim of the investigation, procedures, potential risks or inconveniences and/or expected benefits and have a minimum of 24 hours before deciding on participation. If the subject wishes to consent immediately after receiving information, he may do so and in- and exclusion may be initiated.

The subjects will be informed that their participation is voluntary and that they may leave the investigation at any time, without this having any influence on their further treatment.

The informed consent signature form includes personally dated signatures of the subject and the PI or his/hers representative responsible for conducting the informed consent process. A copy will be provided to the subject.

If new information is to be given during the investigation, sponsor will inform the investigators, and the new information is given to the subjects by the investigator. If new information becomes available that can significantly affect a subject's future health and medical care that information will be provided to the subject in writ-

ten form. The Clinical Manager or delegate is responsible for writing the information and providing it to investigators that will further provide it to the subjects. If applicable, all affected subjects shall be asked to confirm their continuing informed consent in writing.

This procedure also applies to informed consent obtained from a subject's legal representative. The procedure cannot waive the subjects' legal rights.

## 14. Adverse events, serious adverse events and device deficiencies

### 14.1. Adverse event (AE)

An adverse event is any untoward medical occurrence, unintended disease or injury, or untoward clinical signs (including abnormal laboratory findings) that may occur in subjects, users or other parties, whether it is related to the medical device(s), or the procedures involved. This could include events such as headache or dizziness.

## 14.2. Adverse device effect (ADE)

An adverse event, which is related to the use of the investigational medical device, is an adverse device effect, and should be marked as related or possibly related to the medical device(s) on the adverse event form.

The definition of an adverse device effect includes any event resulting from insufficiencies or inadequacies in the instructions for use, malfunction of the device, user error or intentional misuse of the device.

Table 9 lists anticipated adverse device effects that may occur.

ANTICIPATED ADE	FREQUENCY
Urinary tract infection	Improbable
Irritation or minor pain in urethra	
Minor harm to urethra	Improbable
ble 9: Anticinated adverse device offects and their likely f	Improbable

Table 9: Anticipated adverse device effects and their likely frequency rates.

Frequency rates are based on complaint levels received on SpeediCath®Standard Male as well as the risk management file.

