## 2.1.4. Description of the investigational device

The investigational device is a ready-to-use coated catheter for intermittent use (Figure 2).

[figure not shown]

Figure 2: Investigational device

The investigational device is coated with hydrophilic polymers. Each catheter is packed in a foil pouch containing an aqueous solution which serves to hydrate the coating and thus to reduce surface friction of the catheter. This solution is termed the swelling media.

Investigational device: SpeediCath® Standard Male with newly developed swelling media. Comparator: SpeediCath® Standard Male, with existing swelling media.

The only difference between the investigational device and the comparator, lies in the newly developed swellingmedia.

The investigational device resembles the comparator, however, there are small visual/tactile differences why the products cannot be blinded for the nurses (colour of the catheter and swelling media).

The catheter tubes of both devices are made of polyurethane and are both Nelaton catheters (straight) for males, CH 12 in diameter (4.0 mm), approximately 40 cm in length, including connector.

The investigational device is packed the same way as the comparator: Each catheter is packed individually in a foil. Thirty of these are packed in a cardboard box and sterilised using e-beam according EN556. Each box contains an instruction for use (IFU).

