#### **Exclusion Criteria:**

#### Justification for exclusion criteria:

- Abnormalities, diseases or surgical procedures performed in the lower urinary tract
- 2. Symptoms of urinary tract infections (at least one of the following: frequent urination, stinging or pain at urination)
- Participation in any other clinical investigations related to urinary tract system during this investigation (Inclusion → termination)
- 4. Known hypersensitivity toward any of the investigational device

- To ensure a homogeneous group of urinary tracts where abnormalities, diseases or surgical procedures do not influence on the subject's perception of the test catheters.
- 2. To ensure the subject does not have a urinary tract infection at inclusion
- 3. Other investigational procedures may interfere with the endpoints of this investigation
- 4. Ethical reasons and to avoid bias with respect to assessment of the endpoints

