## 14.3. Device deficiency

A device deficiency refers to the inadequacy of the investigational medical device with respect to its identity, quality, durability, reliability, safety or performance. This includes malfunctions, misuse or user errors and inadequate labelling.

Primary and secondary endpoints that are measured during this investigation will not be required to be reported as device deficiencies. Example of a device deficiency could be disconnection of catheter tube to connector.

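### Sections 14.2 and 14.3 define adverse device effect and device deficiency for the investigational device only, so counts and reports under those labels leave out the comparator that every man also receives

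*Combined protocol and SAP*

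**What the plan says.** The plan keeps its two products apart by name. Section 2.1.4 describes the investigational device as the catheter with the new swelling media and then gives the other product: "Comparator: SpeediCath® Standard Male, with existing swelling media". Section 6.2 plans one catheterisation with each product for each of 22 men.

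The basic safety term is neutral between products. Section 14.1 begins: "An adverse event is any untoward medical occurrence, unintended disease or injury, or untoward clinical signs". The narrower terms are not:

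- Adverse device effect (ADE), section 14.2: "An adverse event, which is related to the use of the investigational medical device, is an adverse device effect". The sentence goes on to say that such an event "should be marked as related or possibly related to the medical device(s) on the adverse event form".
- Device deficiency, section 14.3: "A device deficiency refers to the inadequacy of the investigational medical device with respect to its identity, quality, durability, reliability, safety or performance".

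Section 11 (device accountability) is also written around the investigational device, but it closes with "The same accountability procedure will count for the comparator product". Section 14 has no such sentence.

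Exclusion criterion 4 in section 6.3.1 reads: "Known hypersensitivity toward any of the investigational device".

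**The concern.** In a crossover trial of two catheters, a reader expects device-related harm and malfunction to be recorded on the same terms for both. Here the categories that carry device attribution are written for one product only. Two consequences follow if the site applies the text literally.

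First, a listing of ADEs, serious ADEs or deficiencies would show nothing for the comparator by construction, so any entry for the new catheter would look like an excess.

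Second, some information might never be collected. A malfunction need not hurt anyone. Section 14.3 gives separation of the tube from its connector as an example of a deficiency. With the comparator and no harm done, that is neither an AE nor, on the wording, a deficiency. No later analysis plan could recover it.

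The Synopsis gives evaluation of the new catheter's safety and performance as the study aim and lists AEs as a secondary endpoint, so the gap touches a declared purpose of the trial.

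**Working it through.** The plan gives no figure for this point, so the check is to trace each safety term to the definition it rests on.

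| Term or rule | Where | Rests on | Covers the comparator as worded? |
|---|---|---|---|
| AE | 14.1 | Any untoward occurrence | Yes |
| SAE, core criteria | 14.4.1 | AE | Yes |
| SAE report to sponsor (3 days) and to authorities (7 days) | 14.5.1, 14.5.2 | SAE | Yes |
| AE summary | 7.1 | Safety population, exposed to either product | Yes |
| ADE | 14.2 | Relation to the investigational device | No |
| Serious ADE (SADE) and unanticipated serious ADE (USADE) | 14.4.2, 14.4.4 | ADE | No |
| Device deficiency | 14.3 | Inadequacy of the investigational device | No |
| Near-miss deficiency: handling, 3-day and 7-day reports | 14.4.1, 14.5.1, 14.5.2 | Device deficiency | No |
| 10-day report to sponsor | 14.5.1 | ADE and device deficiency | No |

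Three comparator cases show the effect.

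1. *A serious event caused by the comparator.* It is an SAE, reported within 3 days to the sponsor and 7 days to the authorities. Only the SADE label is lost.
2. *A non-serious event caused by the comparator.* It is registered as an AE at the visit, assessed and summarised. It is not an ADE, so the 10-day rule does not reach it, and section 14.5.1 states no other reporting time for non-serious AEs.
3. *A comparator malfunction without harm.* It is not an AE, because nothing untoward happened to anyone, and not a deficiency as worded. The records listed in section 11 cover receipt, identity, expiry, date of use and subject, but not malfunction. No rule in section 14 requires it to be recorded. This holds even if the malfunction could have led to an SAE.

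Share of exposures affected: 22 men × 2 products = 44 planned catheterisations, of which 22 use the comparator; 22/44 = 50%. All 44 are under the AE and SAE rules. The 50% lies outside the ADE and deficiency terms only.

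For illustration, assume the same true device-related event rate p per catheterisation for both products. The expected number of ADEs recorded for the investigational device is 22p, against 0 for the comparator by definition:

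- p = 2%: 22 × 0.02 = 0.44
- p = 5%: 22 × 0.05 = 1.1
- p = 10%: 22 × 0.10 = 2.2

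These rates are assumptions. The documents give none, and the legible frequency entries in Table 9 all describe the anticipated effects as improbable.

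**The case against.** The strongest reply is that little is lost. The secondary endpoint is AEs, not ADEs, and AEs are registered at both catheterisation visits, assessed by the investigator and summarised for anyone exposed to either product. A reader might infer from 14.2 and 14.3 that events caused by the comparator cannot be counted at all, or that the planned safety comparison is biased. The documents do not support either reading. Comparator AEs and SAEs are counted, and section 7.1 plans only a descriptive AE summary with details left to the statistical analysis plan. No safety test and no by-product ADE table is specified. This part of the reply stands.

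It is also said that a comparator event would not have to be marked unrelated, because the form takes relatedness to the medical device or devices in general, and that Table 9 draws its frequencies partly from complaints about the comparator itself. Both suggest loose drafting rather than deliberate exclusion. That is fair, but the phrase about the form tells the site how to mark an event already defined as an ADE. It leaves the scope unclear and does not widen it.

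Thirdly, the product behind each event can largely be recovered, since the sequence is known, each visit uses one product, and accountability records cover both. This stands for AEs. It does not help with a harmless malfunction that nobody was asked to write down.

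Finally, exclusion criterion 4 may simply be a garbled plural. That is plausible, and it is a reason to reconcile the line rather than to read an eligibility gap into it.

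**Conclusion.** The point holds in a limited form. As worded, ADE, SADE, USADE and device deficiency, together with the 10-day and near-miss reporting rules, apply to the investigational device alone. Section 11 shows that the authors knew how to include the comparator and did so there. Any ADE or deficiency count made under these definitions would be one-sided, covering half of the planned catheterisations. A comparator malfunction without harm would fall outside every rule in section 14.

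The severity is minor. AE and SAE capture, SAE reporting and the planned AE summary are intact for both products, and the discomfort endpoint and its non-inferiority analysis are untouched. The conclusion assumes that the site follows the wording literally. If it already treats both catheters alike, the change only brings the text into line with practice. The CRF itself is not in the documents, so whether its forms already carry a product field cannot be judged.

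**What to change.** Add one sentence to section 14, parallel to the one that closes section 11, stating that the definitions of ADE, SADE, USADE and device deficiency, and the reporting rules that depend on them, apply equally to the comparator. State in the statistical analysis plan that ADEs and deficiencies are tabulated by the product used. If the forms do not already identify the product, it can be taken from the visit and the accountability records.

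Reconcile the wording of exclusion criterion 4, in the Synopsis and in section 6.3.1, with the fact that each man receives both products.

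The cost is an amendment of a few lines and perhaps a few more reports from the site. No subjects, visits or procedures are added. The sentence should be in place before enrolment, because malfunctions not recorded at the time cannot be recovered.

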## 14.3. Device deficiency

A device deficiency refers to the inadequacy of the investigational medical device with respect to its identity, quality, durability, reliability, safety or performance. This includes malfunctions, misuse or user errors and inadequate labelling.

Primary and secondary endpoints that are measured during this investigation will not be required to be reported as device deficiencies. Example of a device deficiency could be disconnection of catheter tube to connector.

#### 14.4. Serious adverse events

#### 14.4.1. Serious adverse event (SAE)

A serious adverse event is an adverse event that:

- Led to death.
- Led to a serious deterioration in the health of the subject that either resulted in:
  - 1) a life-threatening illness or injury, or
  - 2) a permanent impairment of a body structure or a body function, or
  - 3) required inpatient hospitalisation or prolongation of existing hospitalisation, or
  - 4) medical or surgical intervention to prevent life-threatening illness or injury or permanent impairment to a body structure or function.
- Led to foetal distress, foetal death or a congenital abnormality or birth defect.

This includes device deficiencies that might have led to a serious adverse event if:

- Suitable action had not been taken, or
- Intervention had not been made, or
- Circumstances had been less fortunate.

These are handled under serious adverse event reporting.

Planned hospitalisation for a pre-existing condition, or a procedure required by the CIP, without serious deterioration in health, is not considered a serious adverse event.

### 14.4.2. Serious adverse device effect (SADE)

A serious adverse device effect is an adverse device effect that has resulted in any of the consequences characteristic of a serious adverse event.

### 14.4.3. Anticipated serious adverse device effect (ASADE)

There are no anticipated serious adverse device effects.

## 14.4.4. Unanticipated serious adverse device effect (USADE)

An unanticipated serious adverse device effect is a serious adverse device effect which by its nature, incidence, severity or outcome has not been identified in the current version of the risk analysis report.

#### 14.4.5. Medical care of subjects

Principal investigator shall ensure that adequate medical care is provided to a subject experiencing an adverse event during and after participation in the clinical investigation. All serious adverse events will be followed until a resolution is addressed.

Subjects are informed to contact investigator if any adverse event should occur during the investigation. Furthermore, investigator will inform the subjects to contact him should serious adverse events occur within one week of the subject is terminated from the study. Subjects are informed to contact their General Practitioner in case of any adverse event(s) happening later than one week of investigation termination.

The status of all ongoing adverse events is documented during site close-out.

## 14.5. Reporting and timelines

## 14.5.1. Investigator's reporting responsibilities

- PI must assess all (S)AE's that occur at his site.
- All serious adverse events and serious adverse device effects must be reported to the sponsor immediately, but no later than 3 calendar days after investigational site study personnel's awareness of the event.
- A device deficiency that could have led to a serious adverse event but did not do so because suitable action was taken, intervention had been made or because of fortunate circumstances should be reported to the sponsor immediately, but no later than 3 calendar days after investigational site study personnel's awareness of the event.
- New findings and/or updates in relation to already reported serious adverse events should also be reported to the sponsor within 3 calendar days after investigator became aware.
- Device deficiencies and all adverse device effects must be reported to sponsor within 10 days.

Device deficiencies and all adverse device effects must be documented immediately and with no undue delay on the safety reporting forms in the CRF.

All the serious adverse events listed above must be reported using the relevant adverse event/serious adverse event/device deficiency form.

Please report to: [contact]

In cases where a mail is not reachable, please call Clinical Manager,

## 14.5.2. Sponsor's reporting responsibilities

It is the responsibility of sponsor to ensure that the following are reported to the relevant authorities immediately, but no later than 7 calendar days following the date of awareness by sponsor.

- All serious adverse events.
- All serious device effects.
- All device deficiencies that could have led to serious adverse events but did not because suitable action was taken, intervention had been made or because of fortunate circumstances.
- New findings and/or updates in relation to already reported events.

If the serious adverse event results in imminent risk of death, serious injury, or serious illness that requires prompt remedial action for other subjects, users or other persons or a new finding to such a serious adverse event, sponsor must immediately but no later than 2 calendar days after awareness by sponsor report the event to national regulatory authorities.

Sponsor must inform all investigators in writing within ten days after the sponsor is made aware, if an AE or Device Deficiency led to corrective actions (e.g change of IFU).

